#### 8.3 Potential benefits

Subjects participating in these studies will receive basic medical and EKG assessments at no cost to them. Otherwise, there are no direct benefits to the subjects participating in this research. The long-term potential benefit of this study is a mechanistically directed approach toward treatment of impulsive aggression arising in serious psychiatric disorders. Every research study requires the potential benefits to outweigh the potential risks of the study. The potential benefit of reducing the burden of impulsive aggression is significant for public health, including for patients, their families, communities, healthcare systems, and criminal justice systems. While the study procedure confers greater than minimal risk, the low likelihood of serious adverse effects is outweighed by the potential public health benefits stemming from the potential results of this study and subsequent studies based on these results.

#### 9 Research alternatives and economic considerations

#### 9.1 Alternatives to participation in the study

This is not a treatment study. Therefore, the study subjects may continue their usual outpatient treatment. If the subject is interested in identifying outpatient treatment options for their psychiatric disorder, the study staff may help the subject identify appropriate locations.

#### 9.2 Payments for participation

All study subjects will be remunerated \$25 for completion of the screening visit, regardless of their decision to enroll in the study or their eligibility to enroll. Because of the crossover nature of the study, subjects only yield meaningful primary outcome data if they complete both testing session. They will therefore be compensated an additional \$100 at the completion of their *second* testing visit. They will *not* be compensated if they only complete one testing visit. This incentivization is designed to yield greater benefit from the research, thereby improving the risk/benefit ratio of the study. Subjects driving a private vehicle will also be reimbursed for travel expenses at the current IRS business mileage rate and reimbursed for four hours of parking or reimbursed for the cost of an entire day of bus fare. Taxi fare or related (i.e. Uber, Lyft) will not be reimbursed. Subjects must provide appropriate receipts to the study staff.

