performed in 5 blocks of 32 trials, with 3 emotional blocks with angry/fearful/sad/disgust faces and 2 non-emotional blocks (Figure 1). Each stimulus is presented for 1 s with a 1 s interstimulus interval. In each block the subject is instructed on the go/no-go targets, each comprising 50% of the task stimuli, with instructions changing at the halfway point in each block. Each block contains two instructions. For example: Emotional blocks: go-angry/nogo-fear or go-fear/nogo-angry; Non-emotional blocks: go-male/nogo-female or go-female/nogo-male (Figure 2). Error rates and reaction times are recorded.

Figure 2 Emotional Go/NoGo schematic. Subjects are given a target instruction at the start of each block for 6 seconds. There is 1 second of blank screen between each 1 second stimulus presentation. In this schematic, the subject would press a key ("Go") when presented with the first stimulus (angry; green border represents the correct response is "Go". This border would not be present in the actual task), and withhold pressing a key for the second stimulus (sad; red border).

Subjects will be monitored for at least 30 minutes after patch removal to confirm the absence of side effects that would compromise their safety upon leaving the hospital.

Subjects will return for day 2 of testing not less than 5 days following day 1. On day 2, subjects will receive the treatment they did not receive on day 1. They will be asked a series of standard questions to assess for the presence of any side effects following their initial study day. If female, they will again be administered a urine pregnancy test to confirm the absence of pregnancy. The remainder of the procedure will be identical to day 1.

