## 8.2 Minimizing Risks

## 8.2.1 Risk of study medication

Dependance: Please see above for a discussion regarding the risk of development of dependence. We chose transdermal delivery of nicotine because its slow rate of delivery significantly reduces the risk of dependence development.

Discomfort: The potential for discomfort will be clearly explained to subjects. Subjects experiencing discomfort who wish to have the patch removed will immediately have their patch removed, and symptoms will subside shortly thereafter. Placebo patches will be handled in exactly the same manner, with the same ability to remove as described above. It should be noted that nicotine patches have been used successfully in populations with cardiovascular disease. Although subjects with known cardiac conduction abnormalities or poorly treated hypertension as assessed during screening will be excluded, these data are reassuring given the possibility of enrolling a subject with a previously undiagnosed cardiovascular condition.

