## 11 Study withdrawal/discontinuation

Subjects may request to withdraw from the study at any time for any reason by contacting the study principal investigator or research team. Requests may be made via email, phone, or in writing, and study coordinator contact information will be provided on the study consent document. If the subject does not provide a reason for discontinuation, the study team will ask the subject if he/she would like to provide a reason for discontinuation, in the hopes to improve subject retention in the future.

Every reasonable effort will be made to maximize subject retention. However, reasons for removal of participants from the study include the following:

- Adverse experience: The participant has experienced an adverse event that, in the opinion of the investigator, requires early termination.
- Death
- Safety risk: Any participant who becomes a safety risk during the trial will be withdrawn.
- Protocol violation: The participant fails to meet protocol entry criteria or did not adhere to protocol requirements.
- Non-compliance: The participant is non-compliant with completion of studyrelated evaluations and or use of study drugs.
- In the investigator's judgment, it is in the participant's best interest to discontinue participation in the treatment/study.
- Consent is withdrawn. The participant wishes to withdraw from the study, or the legally authorized representative wish the participant to be withdrawn.
- Lost to follow up. Participant could not be recalled back to conduct treatment visit(s)

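### Section 9.2 withholds the whole $100 testing payment even from a subject the investigator removes for an adverse event, which gives a financial reason to under-report day 1 side effects

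*Combined protocol and SAP*

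**What the plan says.** Section 9.2 sets two payments. Screening earns $25 "for completion of the screening visit, regardless of their decision to enroll in the study or their eligibility to enroll". Testing earns $100, due "at the completion of their *second* testing visit". For a subject who attends one session the rule is explicit: "They will *not* be compensated if they only complete one testing visit". Travel is reimbursed separately. The reason given is that a crossover yields useful primary outcome data only when both sessions are done: "This incentivization is designed to yield greater benefit from the research".

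Three other sections bear on this rule:

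- **Section 11** gives the right to leave: "Subjects may request to withdraw from the study at any time for any reason". It also lists grounds on which the study may remove a subject. One is "Adverse experience: The participant has experienced an adverse event that, in the opinion of the investigator, requires early termination". Another is becoming a safety risk.
- **Section 6.2** describes the return visit on day 2: "They will be asked a series of standard questions to assess for the presence of any side effects following their initial study day". It also requires at least 30 minutes of observation after the patch comes off.
- **Section 8.2.1** covers discomfort: "Subjects experiencing discomfort who wish to have the patch removed will immediately have their patch removed". It attaches no payment consequence to this, and no section says whether a visit with early patch removal counts as completed.

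The consent pages are not part of the text reviewed, so any softer wording there could not be checked.

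**The concern.** The forfeit in 9.2 is written without regard to why the second visit did not happen. A subject who decides not to come back and a subject whom the investigator withdraws for safety are treated alike. For the first, the rule is an incentive. For the second it cannot change behaviour, because the decision is not the subject's.

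The timing adds to this. Effects that appear after the subject has gone home on day 1 come to the team's notice mainly if the subject mentions them. The one structured occasion for that is the day 2 questioning, when the $100 is still unearned and an adverse event could in principle end participation. What is at stake is the completeness of adverse-event data after day 1. Section 10.1.6 has the principal investigator use those data, after each subject completes, to judge whether the protocol or consent form needs changing.

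**Working it through.** **Inputs**

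- Screening payment $25 and testing payment $100, the latter only on completing visit 2 (section 9.2).
- 25 completers from 30 enrolled with schizophrenia, about 15% dropout, and a healthy control group of similar size (section 12.1).
- Order of treatment block randomised (section 5.4). Each subject receives the other treatment on day 2 (section 6.2).
- Subjects who stopped in the cited non-smoker studies: 1 of 8 on a 15 mg patch (section 8.1.1, where seven of eight continued), and 1 of 8 and 1 of 15 in two four-week studies (same section).

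**Step 1: the plan's own figure.** Enrolment needed = 25 / (1 − 0.15) = 29.4, rounded up to 30. This matches section 12.1. The point does not rest on it.

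**Step 2: size of the forfeit.**

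- Completer: $25 + $100 = $125.
- Subject removed after day 1: $25 plus travel.
- Loss: 100 / 125 = 80% of total pay, and all of the testing pay.

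**Step 3: the chain of rules.**

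1. An adverse event may lead the investigator to end participation (section 11).
2. Ending participation after one session forfeits the $100 (section 9.2, no exception).
3. The structured questions about day 1 come before the $100 is earned (section 6.2).

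A reason to under-report follows from these three together. The documents do not measure whether subjects act on it.

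**Step 4: illustrative count and cost.** Assume 30 controls as well as 30 patients, so about 60 subjects, and equal allocation to the two orders. Then 60 / 2 = 30 wear nicotine on day 1.

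- Low: 30 × 1/15 = 2 subjects, 2 × $100 = $200.
- High: 30 × 1/8 = 3.75, about 4 subjects, 4 × $100 = $400.

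For scale, 50 completers (25 per group, on the same assumption) × $100 = $5,000. The exception would add 200 / 5,000 = 4% to 400 / 5,000 = 8%.

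**Step 5: what cannot be computed.** At 15% dropout, 0.15 × 30 = 4.5, so about 4 to 5 patients would not complete. The documents do not say what share of these would stop after day 1 or because of an adverse event.

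**The case against.** The rule is deliberate and explained. A crossover needs both sessions, the $25 and travel are kept, and a completion payment is a reasonable way to limit missing second periods. That stands, and it is why the incentive should stay for subjects who simply do not return.

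Several stronger readings are tempting, but the documents do not support them:

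- *That the rule undercuts the patch-removal protection.* Section 8.2.1 grants removal on request and links it to no payment. The protocol is silent on whether such a visit counts as completed. That is a gap to close, not a contradiction.
- *That safety data rest on self-report alone.* Section 8.2.5 describes close monitoring on both study days, and section 6.2 requires observation after patch removal. The incentive bears on effects that arise later.
- *That reporting a side effect costs the subject the payment.* Removal requires the investigator to judge that the event calls for it.
- *That an unwell subject would sit through a second nicotine session to be paid.* A subject with nicotine effects on day 1 receives placebo on day 2. Only someone with an event after day 1 placebo would go on to nicotine.
- *That the stop rates should be applied to all 60 subjects.* Only about half wear nicotine on day 1. Stops during a day 2 nicotine session fall under the completed-visit gap instead.

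The rates themselves are also a poor match. They come from a 15 mg patch and from four-week regimens worn 16 hours a day, whereas this study applies one 7 mg patch and removes it after a task that starts no later than 120 minutes after placement. Section 8.1.1 also reports excellent tolerability in a larger nicotine study. The count is an illustration only.

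**Conclusion.** The point holds in a limited form. As written, a subject removed by the investigator after day 1 for an adverse event or safety risk loses $100 of $125, and no section available for review makes an exception. The stated rationale does not reach that subject, and the placing of the day 2 questions gives a reason to under-report later effects. That last step is inferred from the rules.

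The size is small: about 2 to 4 subjects and $200 to $400. This assumes 30 controls, equal allocation to order, and stop rates carried over from other doses and durations. The argument does not depend on the count. The matter concerns fairness of payment and adverse-event ascertainment, and it leaves the sample size, power and primary analysis unchanged. It is a low-priority, inexpensive improvement.

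**What to change.** Keep the $100 completion payment as it is for subjects who choose not to return. Add to section 9.2, and to the consent form if it does not already say so, that:

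1. a subject whose participation the investigator ends because of an adverse event or on safety grounds receives the full testing payment; and
2. a testing visit in which the patch is removed early counts as completed for payment.

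The cost is a short wording change and, on the assumptions above, a few hundred dollars. Slightly more early stops may be reported. No dose, schedule or clinical rule changes.

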## 9.3 Costs for participation

As noted above, subjects will be reimbursed for travel to the study site. All procedures will be provided to subjects at no cost. This includes an electrocardiogram, as described above in detail. Study drug will be provided at no cost.

## 9.4 Medical treatment in case of injury

If it is determined by Vanderbilt and the Investigator that an injury occurred as a direct result of the tests or treatments that are done for research, the subject will be provided immediate medical care at Vanderbilt to treat the injury at no cost to the subject or the subject's insurance. In the absence of an immediate need for medical care, there will be no additional medical treatment available to subjects above and beyond what was available prior to initiating the study. Either licensed physicians or study staff working directly with licensed physicians will conduct the study visits. Emergency medical treatment is available at VUMC. less than one block from VPH. All study subjects will be able to contact study staff throughout their enrollment in the study. Study subjects will be informed regarding the policy noted above. Subjects will obtain treatment either from their current outpatient physicians or via emergency medical services, as recommended by the study physician. There are no limits to the treatment provided. Treatment decisions will be made entirely by the patient's outpatient physician or emergency medical provider and will not be affected by the individual's participation in the study. This is clearly described in the consent form. Study subjects will have the contact information of a licensed study physician at all times who will be available for consultation to determine whether the patient should seek medical treatment during the study.

# 10 Reporting of adverse events or unanticipated problems involving risk to participants or others

The investigator's assessment of the overall risk level for subjects participating in this study is moderate.

The risks associated with the current study are deemed greater than minimal for the following reasons:

- 1. We do not view the risks associated with transdermal nicotine administration as minimal risks.
- 2. Given the established safety of transdermal nicotine in prior work, we do not view the proposed studies as high risk.

Although we have assessed the proposed study as one of greater than minimal risk, the potential exists for anticipated and/or unanticipated adverse events, serious or otherwise, to occur since it is not possible to predict with certainty the absolute risk in any given individual or in advance of first-hand experience with the proposed study methods. Therefore, we provide a plan for monitoring the data and safety of the proposed study as follows:

## 10.1 Greater than minimal risk Data and Safety Monitoring Plan

## 10.1.1 Personnel responsible for the safety review and its frequency

The principal investigator, [name]., Ph.D., will be responsible for monitoring the data, assuring protocol compliance, and conducting the safety reviews at the specified frequency, which must be conducted at a minimum of every 6 months (including when reapproval of the protocol is sought). He will perform this duty in close consultation with his academic mentors, [name]. and [name]. During the review process, the principal investigator will evaluate whether the study should continue unchanged, require modification/amendment, or close to enrollment. The principal investigator ([name]), mentors (Drs. [name] and [name]), or the IRB have the authority to stop or suspend the study or require modifications. A review of the study will be submitted annually to the Vanderbilt Human Research Protections Program (HRPP)/IRB as well as to the NIMH included in the annual progress report

## 10.1.2 Attribution of adverse events

Adverse events will be monitored for each subject participating in the study and attributed to the study procedures / design by the principal investigator ([name]., Ph.D.) according to the following categories:

- 1. Definite: Adverse event is clearly related to investigational procedures(s)/agent(s).
- 2. Probable: Adverse event is likely related to investigational procedures(s)/agent(s).
- 3. Possible: Adverse event may be related to investigational procedures(s)/agent(s).
- 4. Unlikely: Adverse event is likely not to be related to the investigational procedures(s)/agent(s).
- 5. Unrelated: Adverse event is clearly not related to investigational procedures(s)/agent(s).

## 10.1.3 Plan for grading adverse events

The following scale will be used in grading the severity of adverse events noted during the study:

- 1. Mild adverse event
- 2. Moderate adverse event
- 3. Severe

## 10.1.4 Plan for determining seriousness of adverse events

#### Serious Adverse Events:

In addition to grading the adverse event, the PI will determine whether the adverse event meets the criteria for a Serious Adverse Event (SAE). An adverse event is considered serious if it results in any of the following outcomes:

- 1. Death;
- 2. A life-threatening experience in-patient hospitalization or prolongation of existing hospitalization;
- 3. A persistent or significant disability or incapacity;

- 4. A congenital anomaly or birth defect; OR
- 5. Any other adverse event that, based upon appropriate medical judgment, may jeopardize the subject's health and may require medical or surgical intervention to prevent one of the other outcomes listed in this definition.

An adverse event may be graded as severe but still not meet the criteria for a Serious Adverse Event. Similarly, an adverse event may be graded as moderate but still meet the criteria for an SAE. It is important for the PI to consider the grade of the event as well as its "seriousness" when determining whether reporting to the IRB is necessary.

## 10.1.5 Plan for reporting Unanticipated Problems Involving Risks to Subjects or Others (UPIRSOs, including Adverse Events) to the IRB

The principal investigator will report the following types of events to the IRB:

Any incident, experience or outcome that meets ALL 3 of the following criteria:

- Is unexpected (in terms of nature, specificity, severity, or frequency) given (a) the research procedures described in the protocol-related documents, such as the IRB-approved protocol and informed consent document and (b) the characteristics of the subject population being studied; AND
- 2. Is related or possibly related to participation in the research (*possibly related* means there is a reasonable possibility that the incident, experience, or outcome may have been caused by the procedures involved in the research); AND
- 3. Suggests that the research places subjects or others at greater risk of harm (including physical, psychological, economic, legal, or social harm) than was previously known or recognized.

Unanticipated Problems Involving Risks to Subjects or Others (UPIRSOs) may be medical or non-medical in nature, and include – but are not limited to – *serious, unexpected, and related adverse events* and *unanticipated adverse device effects. Adverse* events will be reported to the IRB as UPIRSOs **only** if they meet all 3 criteria listed above.

These UPIRSOs/SAEs will be reported to the VU IRB/HRPP via telephone. All related events involving risk but not meeting *prompt* reporting requirements will be reported to the IRB in summary form at the time of continuing review. If appropriate, such summary may be a simple brief statement that events have occurred at the expected frequency and level of severity as previously documented.

10.1.6 Plan for reporting adverse events to co-investigators on the study, DSMBs, study sponsors, funding and regulatory agencies, and regulatory and decision-making bodies.

The following individuals, funding, and/or regulatory agencies will be notified:

• All Co-Investigators listed on the protocol.

• National Institutes of Health/National Institute of Mental Health. Notification will be to the attention of the Program Official assigned to the award supporting this study, [name]., [contact], [contact].

The principal investigator ([name]., Ph.D.) will conduct a review of all adverse events upon completion of every study subject. The principal investigator will evaluate the frequency and severity of the adverse events and determine if modifications to the protocol or consent form are required.

## 11 Study withdrawal/discontinuation

Subjects may request to withdraw from the study at any time for any reason by contacting the study principal investigator or research team. Requests may be made via email, phone, or in writing, and study coordinator contact information will be provided on the study consent document. If the subject does not provide a reason for discontinuation, the study team will ask the subject if he/she would like to provide a reason for discontinuation, in the hopes to improve subject retention in the future.

Every reasonable effort will be made to maximize subject retention. However, reasons for removal of participants from the study include the following:

- Adverse experience: The participant has experienced an adverse event that, in the opinion of the investigator, requires early termination.
- Death
- Safety risk: Any participant who becomes a safety risk during the trial will be withdrawn.
- Protocol violation: The participant fails to meet protocol entry criteria or did not adhere to protocol requirements.
- Non-compliance: The participant is non-compliant with completion of studyrelated evaluations and or use of study drugs.
- In the investigator's judgment, it is in the participant's best interest to discontinue participation in the treatment/study.
- Consent is withdrawn. The participant wishes to withdraw from the study, or the legally authorized representative wish the participant to be withdrawn.
- Lost to follow up. Participant could not be recalled back to conduct treatment visit(s)

